Abbreviations: CBC, complete blood count; CT, computerized tomography; EKG, electrocardiogram; MRI, magnetic resonance imaging; PSA, prostate-specific antigen; Mos, Month

1. All evaluations should be conducted within 30 days prior to registration/randomization. The exception to this is the radiologic evaluations and informed consent, which can be performed within 90 days prior to day 1.
2. CBC which includes WBC (with differential), platelets, Hgb, and Hct
3. Chemistries include albumin, alkaline phosphatase, total bilirubin, BUN, calcium, chloride, creatinine, glucose, sodium, potassium, total protein, SGOT [AST], and SGPT [ALT].
4. Those patients coming off study prior to PSA progression (i.e. for toxicity, etc.) should be evaluated for PSA levels every 3 months until PSA progression occurs.
5. ECGs may also be performed as clinically indicated throughout the study.
6. Radiologic evaluations (CT/MRI and bone scan) and chest x-ray (if applicable) should be conducted at PSA progression. Scans can also be obtained sooner as clinically indicated.
7. Quality-of-life (QoL) tools will include FACT-P, EORTC QLQ-C30/QLQ-PR25, and SHIM.
8. Patients should remain on study until PSA progression. This is defined as a PSA value ≥ 0.2 ng/mL above nadir that is confirmed by a second consecutive PSA value ≥ 8 weeks later which is higher (and ≥ 0.4 ng/mL). Patients should remain on study until the confirmatory PSA.
9. The total length of the study is 18 months for full enrollment and 24-months of follow-up for the last patient or 42 months. Patients who have 24-months of follow-up following treatment will continue to be followed for PSA determinations only and should remain on study until PSA progression or study end at month 42 whichever comes first.
10. To be conducted 2 months after the patient comes off study.
11. In patients who have consented, a tumor tissue block should be requested for banking, preferably from the prostatectomy specimen. If not available, a tissue block from the prostate biopsy should be submitted. In addition, a normal tissue block from the same patient (preferably from the prostatectomy) should be requested for banking. This only applies to the lead site (JHU).
12. Drug and diary review and dispensing may be done prior to or indicated day.
13. SRT to start 61 days (+/- 3 weeks) after Day 1. SRT will be delivered Monday-Friday
14. Decipher Test can be completed at any time before treatment ends on Day 180.

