Dose reduction for enzalutamide or placebo will be allowed. If a patient experiences a \geq Grade 3 toxicity or an intolerable side effect, withhold dosing for one week or until symptoms improve to \leq Grade 2, then resume at the same or a reduced dose (120 mg or 80 mg).

Any toxicity requiring enzalutamide discontinuation will be recorded as an AE in the subject's medical record and on the CRF.

5.4.1 *Seizures*

Seizures that occur at any time during the study, regardless of causality, severity, or outcome, will result in enzalutamide discontinuation and be recorded in the subject's medical record and on the CRF.

5.5 **End of Treatment/Treatment Discontinuation Visit (+/- 30 days from last dose)**

The following procedures are to be conducted every 3 months ± 1 month up to 24 months (see Table 1):

- Review concurrent medications (see Appendix B for a listing of medications with the potential for drug interactions)
- Physical exam (vital signs, weight)
- ECOG performance status (Appendix A)
- Adverse events evaluation
- Laboratory tests (CBC w/diff, PSA, testosterone, comprehensive chemistry panel, including bilirubin, creatinine, SGOT[AST], SGPT[ALT])
- QoL questionnaires
- Decipher Test (Will only be completed once before treatment ends on Day 180. This test will not be repeated.)

5.6 **Follow-up (Every 3 months for ≥ 24 months or until death)**

Patients will be followed for ≥ 2 years (and up to 42 months total) after removal from treatment or until death. Patients withdrawn from the study because of AEs will be followed until the adverse event has either resolved or stabilized. Reasons for premature withdrawal should be determined and noted.

Freedom-from-PSA-progression (FFPP) is the primary objective and is defined as the time from randomization to the date of PSA progression. A subject who does not have PSA progression at the time of the analysis will be censored at the last date of PSA measurement. In patients who achieve an undetectable PSA value (defined as ≤ 0.1 ng/mL), PSA progression is defined as a detectable PSA value (≥ 0.2 ng/mL) that is confirmed by a second consecutive PSA value obtained ≥ 8 weeks later which is higher (and ≥ 0.4 ng/mL). In patients who do not achieve an undetectable PSA, PSA progression is defined as a 0.2 ng/mL increase from nadir that is confirmed by a second consecutive PSA value obtained ≥ 8 weeks later which is higher.

5.7 **Concomitant Medications**

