Because of the potential for drug-drug interaction, the concurrent use of all other drugs, over-the-counter medications, or alternative therapies must be documented on the case report form (CRF). The principal investigator should be alerted if the patient is taking any agent found in Appendix B (a listing of medications with the potential for drug-drug interactions).

5.7.1 *Supportive Care Medications*

Subjects should receive full supportive care, including transfusions of blood and blood products, antibiotics, antiemetics, or other therapies, in accordance with standard practice at the clinical trial site.

All concomitant medications administered from screening through the post-treatment visit, including indication, dose, route, frequency and treatment dates, will be recorded in the subject's medical record and on the CRF. After the post-treatment visit, only anticancer therapies will be recorded.

5.7.2. *Prohibited before enrollment and during administration of study treatment*

- Any therapy for prostate cancer except for that radical prostatectomy and those administered in this protocol.
- Strong inducers or inhibitors of CYP2C8 (gemfibrozil, rifampin [see examples in Appendix B]).
- Medications that are metabolized by CYP3A4, CYP2C9, or CYP2C19 that have a narrow therapeutic index (see examples in Appendix B).
- Strong inducers or inhibitors of CYP3A4 (including but not limited to phenytoin, carbamazepine, rifampin, rifabutin, rifapentine, and phenobarbital [see examples in Appendix B]).
- Medications that may lower seizure threshold as determined by the investigator.

5.7.3 *Drugs that may affect exposure to Enzalutamide*

The principal investigator should be alerted if the patient is taking any agent found in Appendix B (a listing of medications with the potential for drug-drug interactions).

Refer to the following links for updated lists of CYP inhibitors, inducers, and substrates:

- <http://www.fda.gov/Drugs/DevelopmentApprovalProcess/DevelopmentResources/DrugInteractionslabeling/ucm093664.htm#potency>
- <http://medicine.iupui.edu/clinpharm/ddis/table.aspx>

Drugs That Inhibit or Induce CYP2C8

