8.1.2 Secondary endpoints

The first secondary endpoint is time to local recurrence within the radiation field, defined as the time from randomization to the date of local recurrence of disease. Subjects who do not have local recurrence will be censored on the date of their last evaluable tumor assessment for local recurrence. Subjects who start any subsequent anti-cancer therapy without a prior reported local recurrence will be censored at the last evaluable tumor assessment prior to initiation of the subsequent anti-cancer therapy.

The second secondary endpoint is radiographic metastasis free survival (rMFS), defined as the time from randomization to the date of metastasis or death from any cause, whichever occurs first. A subject who does not have metastasis and is alive will be censored at the last date of tumor assessment. We will pay particular attention to the 2-year MFS rate.

Safety and tolerability will also be evaluated as secondary objectives.

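### Table 1 takes men off study at confirmed PSA progression with no later tumor assessment, Section 5.6 says otherwise, and the 2-year MFS rate would be sparse and biased

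*Combined protocol and SAP*

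**What the plan says.** **Exit rule.** Table 1 footnote 8: "Patients should remain on study until PSA progression", then "Patients should remain on study until the confirmatory PSA". Footnote 9 says that men past 24 months "will continue to be followed for PSA determinations only" until PSA progression or study end. Footnote 4 keeps 3-monthly PSA going only for men who come off study before progression, and stops it at progression.

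**Imaging.** Table 1 marks CT/MRI, chest X-ray and bone scan after baseline only in the Off-Study column. Footnote 6: "Radiologic evaluations (CT/MRI and bone scan) and chest x-ray (if applicable) should be conducted at PSA progression", with the allowance that "Scans can also be obtained sooner as clinically indicated".

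**The other rule.** Section 5.6: "Patients will be followed for ≥ 2 years (and up to 42 months total) after removal from treatment or until death". It does not stop at PSA progression. It names no imaging and no metastasis assessment, and the only endpoint it describes is FFPP. Section 5.2 schedules 3-monthly visits to 24 months, also without a stop at progression, and accepts outside records, telephone, email or mail.

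**Endpoints.** Sections 8.1.2 and 10.1.2 censor MFS at the last tumor assessment. Section 8.1.2 counts every death and adds "We will pay particular attention to the 2-year MFS rate". Section 10.1.2 counts a death only within 90 days of the last response assessment. Local recurrence must be confirmed pathologically (synopsis, Section 2.2). It is censored at the last evaluable assessment, or at the last one before any later anticancer therapy.

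**The concern.** Section 8.1.1 treats a rising PSA as the first sign of relapse, so metastasis and in-field recurrence are expected mostly after it. A site following Table 1 stops looking just as that risk starts. The exit is itself the primary event and is assumed to occur twice as often in the control arm by month 24. Kaplan-Meier censoring assumes that a man who leaves has the same later risk as those who remain, which is implausible for a man leaving because his PSA has risen.

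At stake are MFS, with its 2-year rate, and time to local recurrence. These are the only clinical efficacy results beyond PSA in a trial meant to inform a phase III study. A site following Section 5.6 would collect different data from one following Table 1. Dates not collected after progression may not be recoverable later.

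**Working it through.** **Inputs.** 2-year FFPP 60% (Arm A) and 80% (Arm B), exponential times, one-sided alpha 0.1, power 90%, 39 events (Section 10.4.1). 48 men per arm, accrual 60 months plus 21 months of follow-up (revised-design table). Confirmation at least 8 weeks after the first rise (endpoint definition).

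**The plan's own figure.** HR = ln 0.8 / ln 0.6 = 0.437, stated as 0.44. Schoenfeld events = 4 × (1.2816 + 1.2816)² / (ln 0.44)² = 39. The stated design reproduces. The documents give no corresponding figure for MFS.

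**1. Men reaching PSA progression by month 24.**
- Arm A: 48 × 0.40 = 19.2. Arm B: 48 × 0.20 = 9.6. Total 28.8 of 96.
- Allowing 8 weeks (1.84 months) for confirmation, a man has left by month 24 if his first rise came by month 22.16. Arm A: 48 × (1 − 0.6^(22.16/24)) = 18.0. Arm B: 48 × (1 − 0.8^(22.16/24)) = 8.9.

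**2. Observation lost before month 24** (confirmation delay ignored). Monthly hazards are λ = −ln 0.6 / 24 = 0.02128 (A) and −ln 0.8 / 24 = 0.00930 (B). Mean loss per man = 24 − (1 − e^(−24λ)) / λ.
- Arm A: 24 − 0.40 / 0.02128 = 5.21 months, or 22% of 24; 13.0 months per progressor.
- Arm B: 24 − 0.20 / 0.00930 = 2.49 months, or 10% of 24; 12.4 months per progressor.

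**3. Men without progression.** With uniform accrual, follow-up runs from 21 to 81 months. The share never progressing in follow-up is (e^(−21λ) − e^(−81λ)) / (60λ): 0.361 (A) and 0.630 (B), that is 17.3 and 30.3 men. If scans happen only at PSA progression, these men have no post-baseline scan and are censored for MFS at baseline.

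**4. Men still at risk for MFS at month 24.** 95% of men have more than 24 months of potential follow-up, since (81 − 24) / 60 = 0.95.
- If every man had an off-study scan: 48 × 0.95 × 0.6 = 27.4 (A) and 48 × 0.95 × 0.8 = 36.5 (B).
- If only progressors are scanned, subtract men followed beyond 24 months who never progress, 48 × (e^(−24λ) − e^(−81λ)) / (60λ) = 15.8 (A) and 28.3 (B). This leaves 11.5 and 8.2.

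**5. Direction of bias (illustration; metastasis rates are assumed, not in the documents).** Let p be the chance that the progression scan is positive. Other progressors develop metastases after an exponential delay with the median shown. Two censoring readings, with progressors leaving at progression in both:
- Non-progressors censored at baseline: the 2-year Kaplan-Meier value tends to (11.5/30.7)^p in A and (8.2/17.7)^p in B. The denominators are the expected progressors, 48 − 17.3 and 48 − 30.3.
- Non-progressors treated as followed: it tends to 0.6^p and 0.8^p.

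True 2-year MFS = 1 − p(1 − e^(−24λ)) − (1 − p)F. Here μ = ln 2 / median and F = 1 − (μe^(−24λ) − λe^(−24μ)) / (μ − λ).

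| Assumption | Arm | True | Censored at baseline | Treated as followed |
|---|---|---|---|---|
| p = 5%, median 24 months | A | 0.866 | 0.952 | 0.975 |
| | B | 0.935 | 0.962 | 0.989 |
| p = 10%, median 96 months | A | 0.928 | 0.907 | 0.950 |
| | B | 0.965 | 0.925 | 0.978 |

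With baseline censoring the estimate is too high in both arms under the first assumption and too low in both under the second. With non-progressors treated as followed it is too high throughout.

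**The case against.** The strongest reply is that the documents do not clearly end data collection at progression. Section 5.6 follows men until death, Section 5.2 has 3-monthly visits with no stop at progression, and footnote 4 shows that off study does not always mean out of contact. Footnote 10 mentions something 2 months after a man comes off study, though no procedure can be tied to it in the extracted table. Section 5.7.1 adds "After the post-treatment visit, only anticancer therapies will be recorded". Section 10.2.1 lists time to restarting hormonal therapy as an efficacy endpoint, which needs data past progression. These are also unpowered secondary endpoints in a phase II trial.

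Much of this stands, and it rules out four stronger readings that a reader might infer:
- **Deaths after progression go uncaptured.** Not established, since Section 5.6 could capture them. What is established is the conflict, and that under Section 10.1.2 a captured death might still not count.
- **The 2-year MFS rate cannot be estimated.** It can be computed. The trouble is reliability.
- **MFS will look too good in both arms, more so in Arm A.** The illustration shows that the direction depends on how non-progressors are censored and on rates the documents do not give.
- **Local recurrence reduces to what one scan shows.** It needs pathological confirmation, so a scan alone cannot create an event.

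What does not stand is the idea that Section 5.6 cures the problem. It schedules no tumor assessment, and MFS is censored at the last one.

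**Conclusion.** The point holds as an unreconciled follow-up rule with a real effect on the secondary endpoints. Under Table 1 no tumor assessment is scheduled after PSA progression, and none before it unless clinically indicated. About 19 (A) and 10 (B) of 48 men progress by month 24; about 18 and 9 have left once confirmation is allowed for. Censoring of MFS would then depend on the primary outcome and fall about twice as often on control. Between 11.5 and 27.4 men in Arm A, and between 8.2 and 36.5 in Arm B, would be at risk at month 24, depending on whether non-progressors are ever scanned.

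The counts rest on the plan's FFPP rates, exponential times, uniform accrual and no dropout, with month 42 in footnote 9 not applied as a cap for each man; a cap would leave more men unscanned. They count men, not lost MFS events, for which the documents give no rate. The primary FFPP analysis is unaffected, so the change is advisable rather than critical.

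**What to change.** 1. Reconcile footnotes 6, 8 and 9 with Section 5.6 so that confirmed PSA progression ends the FFPP assessment only.
2. Follow every man, progressed or not, to study end for dates of metastasis, pathologically confirmed local recurrence, subsequent anticancer therapy and death. Use standard-of-care imaging, outside records or telephone. Section 5.2 already allows these routes up to 24 months; extend them beyond that. Add no protocol scans.
3. Give MFS one definition in Sections 8.1.2 and 10.1.2, counting all deaths during follow-up and dropping the 90-day limit.
4. Align the censoring rules with the longer follow-up, for non-progressors as well. One workable choice for MFS is to censor at the last contact with no known metastasis, with censoring at the last tumor assessment as a sensitivity analysis. Revisit the rule that censors local recurrence at later therapy, or newly collected events would still be excluded.

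Cost: an amendment and a short periodic form, mainly extra work for the roughly 39 men with progression. Downsides are modest site data entry and imaging timed by clinical practice, so metastasis dates will be less regular than with scheduled scans.

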- Patients must be disease-free from prior malignancies for ≥ 3 years, with the exception of non-melanoma skin cancers and superficial urothelial cancers.
- Patients must have the ability to swallow the study drug whole as a tablet or capsule.
- Willingness to use adequate methods of contraception throughout study participation and for at least 3 months after completing therapy
- The patient was informed about the positive survival results of the RTOG 96-01 clinical trial, and has elected to forgo treatment with high-dose bicalutamide

Study centers Six sites in the United States, including the lead site (SKCCC, Johns Hopkins University)

Start date/Duration First patients are expected to be enrolled in March 2015. Accrual has been slower than originally estimated but we will end accrual March 2020 with additional 21 months of follow-up after the last patient has been entered.

Expected enrollment 96 patients

Rationale The primary hypothesis of this study is that outcomes for patients with biochemically recurrent prostate cancer following radical prostatectomy will be improved by the addition of enzalutamide

for 6-months compared to standard-of-care salvage radiation therapy to allow for further study in the definitive phase III setting. This study builds on the prior success of high-dose bicalutamide (for 24 months) when combined with salvage XRT, while using a newer more potent anti-androgen for a shorter duration of time (6 months) in an effort to minimize adverse effects.

[figure not shown]
Objectives Primary

The primary objective of the study is to evaluate the efficacy of the two treatment regimens in terms of freedom-from-PSA-progression (FFPP). FFPP is defined as the time from randomization to the date of PSA progression. In patients who achieve an undetectable PSA value (defined as ≤ 0.1 ng/mL), PSA progression is defined as a detectable PSA value (≥ 0.2 ng/mL) that is confirmed by a second consecutive PSA value obtained ≥ 8 weeks later which is higher (and ≥ 0.4 ng/mL). In patients who do not achieve an undetectable PSA, PSA progression is defined as a 0.2 ng/mL increase from nadir that is confirmed by a second consecutive PSA value obtained ≥ 8 weeks later which is higher.

Secondary

- Time to local recurrence within the radiation field (confirmed pathologically).

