5.2 Treatment Period

The following procedures are to be conducted each study visit on visit on Day 1, 61, 91, 120, 151 and 180 days while on study. Day 1, 61, 120 procedures should be done within seven days prior; day 91, 151 and 180 procedures should be done +/- 14 days (see Table 1):

- Review concurrent medications (see Appendix B for a listing of medications with the potential for drug interactions)
- Physical exam (vital signs, weight)
- ECOG performance status (Appendix A)
- Adverse events evaluation
- Review pill diary
- Laboratory tests (CBC w/diff, PSA, testosterone, comprehensive chemistry panel, including bilirubin, creatinine, SGOT[AST], SGPT[ALT])
- QoL questionnaires

The following procedures are to be conducted at each follow-up visit every 3 months ± 1 month up to 24 months (see Table 1). If participants are unable to return for follow-up, outside records may be obtained and assessments may be conducted via phone, email, or mail when possible:

- Review concurrent medications (see Appendix B for a listing of medications with the potential for drug interactions)
- Physical exam (vital signs, weight)
- ECOG performance status (Appendix A)
- Adverse events evaluation
- Laboratory tests (CBC w/diff, PSA, testosterone, comprehensive chemistry panel, including bilirubin, creatinine, SGOT[AST], SGPT[ALT])
- QoL questionnaires

The following procedure is to be conducted at each follow-up visit every 3 months ± 1 month past the first 24 months and up to 42 months (see Table 1):

- Laboratory test (PSA)

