10.4.1 Sample size calculation

Based on the largest multi-institutional SRT series published (n=1,540) in which patients received SRT followed by observation until the PSA reached ≥ 0.2 ng/mL above the post-SRT nadir, the 2-year FFPP was approximately 60% with SRT. For our primary endpoint of 2-year FFPP we expect an absolute 20% improvement with the treatment of SRT+ enzalutamide (2-year FFPP 80%) over SRT alone (2-year FFPP 60%).

We originally assumed an accrual time of 18 months, with ≥ 24 months of additional follow-up time. FFPP at 2 year from 60% to 80%, a 20% increase (corresponding to a hazard ratio of 0.44 under the assumption of exponential distribution of event times) corresponds to 39 events total of PSA progression (for example 26 in Arm A, and 13 in Arm B) with a 90% power to detect an improvement of, using a one-sided log-rank test at significance level 0.1. Adjusting for 15% non-evaluable or dropout patients, we will randomize a total of 122 patients (61 patients in each arm).

The power of the study is driven by the number of PFS progression events. The design requires 39 events when the analysis of the primary endpoint is conducted. Under the assumption that there are not non-evaluable patients or no dropout, a total of 102 patients needs to be enrolled over 18 months with ≥ 24 months of additional follow-up to reach 39 events. Because the study duration is as long as 3.5 years, a fair number of patients may be lost to follow-up before that and their time to PSA progression will be censored at the last date of PSA measurement. So we assume a non-evaluable and loss-to-follow-up rate of 15% when we estimate the total number of participants.

The trial started enrolling patients in April 2015, and has enrolled 80 patients by April 2019. The rate of accrual is about 10 patients every 6 months. Due to slower than expected enrollment, we propose to extend the accrual time to the end of March 2020. We plan to conduct the primary analysis when 39 events occur.

Our new efficacy assumption stays the same as to detect the difference of Freedom From PSA Progression (FFPP) at 2 year from 60% in SRT+placebo arm to 80% in SRT+enzalutamide arm, a 20% increase (corresponding to a hazard ratio of 0.44 under the assumption of exponential distribution of event times.) The study power remains at 90% with one-sided type I error 0.1 using log-rank test.

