The sample size is 96 total (48 per arm) accounting for 15% loss-to-follow up before PSA progression events. Below represents the new enrollment target for patients given this revised power calculation based on number of events thus far, follow-up and drop out to date.

Total number of PSA progression events	Sample size	Planned accrual time (mons)	Additional follow-up time (mons)	End of accrual	End of follow-up (start the analysis)	Power
Original design						
39	122 (61 per arm)	18	24			90%
New design						
39	96 (48 per arm)	60	21	March 2020	Dec. 2021	90%

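### PSA follow-up is still capped at 42 months, a figure from the superseded 18+24-month design, although the revised 60+21-month, 39-event design needs later events

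*Combined protocol and SAP*

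**What the plan says.** **Follow-up schedule.** Footnote 9 of Table 1 shows where its limit comes from: "The total length of the study is 18 months for full enrollment and 24-months of follow-up for the last patient or 42 months". It then directs that men who have completed 24 months of follow-up "should remain on study until PSA progression or study end at month 42 whichever comes first". Section 5.2 schedules PSA-only visits "every 3 months ± 1 month past the first 24 months and up to 42 months". Section 5.6 uses a different clock: "Patients will be followed for ≥ 2 years (and up to 42 months total) after removal from treatment or until death". Footnote 8, attached to the same Table 1 column, has no month limit: "Patients should remain on study until PSA progression". That column is headed as running to the end of the study.

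**Current design.** The synopsis says "we will end accrual March 2020 with additional 21 months of follow-up after the last patient has been entered". The design table in section 10.4.1 labels 18+24 months the original design. The new design has 60 months of accrual, 21 further months and analysis in December 2021. The analysis trigger is an event count: "We plan to conduct the primary analysis when 39 events occur". On size: "The sample size is 96 total (48 per arm) accounting for 15% loss-to-follow up before PSA progression events".

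**End of study.** Section 9.6 locks the database 24 months after the last enrolment, against 21 months in the synopsis and section 10.4.1.

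**The concern.** Under the original design the limit was harmless. The first patient in could be followed for at most 18 + 24 = 42 months, so it could not remove an event. Under the revised design potential follow-up runs from 21 to 60 + 21 = 81 months, and with uniform accrual (81 − 42)/60 = 65% of patients could pass month 42. The limit now binds on most of the trial.

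Section 10.4.1 itself says power is driven by the number of progression events. A site following the calendar as written would stop PSA measurement in men who are still progression-free and at risk for the primary endpoint. Because the three places start the clock differently, sites could also stop at different times. Two related gaps make this worse: the end of follow-up is given as both 21 and 24 months after the last patient, and no rule says what to do if December 2021 arrives with fewer than 39 events.

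**Working it through.** **Inputs (section 10.4.1 unless stated).** Two-year FFPP 60% versus 80%, exponential; one-sided alpha 0.10; power 90%; 1:1 allocation; 96 patients; 15% loss; accrual 60 months plus 21. Uniform accrual is my assumption. Drug is given for 6 months (section 5.2.1), so 42 months after treatment is about 48 months from randomization.

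**1. Reproduce the plan's figures.**
- Monthly hazards: λ_A = −ln(0.6)/24 = 0.02128; λ_B = −ln(0.8)/24 = 0.00930. HR = 0.437 (plan: 0.44).
- Schoenfeld events: 4 × (1.2816 + 1.2816)² / (ln 0.437)² = 38.3, so 39, as stated.
- Original design, 102 patients over 18+24 months: 25.6 + 13.4 = 39.0 expected events, matching the plan's 39 (its example is 26 + 13).

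**2. Revised design, with and without the limit.** First take the 15% as contributing nothing: 96 × 0.85 = 81.6 evaluable, 40.8 per arm. Expected events = 40.8 × Σ over arms of the mean of [1 − exp(−λ × min(t, cap))], with t uniform on 21–81 months. Power = Φ(√d/2 × |ln HR| − 1.2816). The chance of at least 39 events is from 100,000 simulated trials of 82 evaluable patients.

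| Follow-up rule | Mean event probability, A / B | Expected events by Dec. 2021 | Power | Chance of ≥ 39 |
|---|---|---|---|---|
| To the cutoff | 0.639 / 0.370 | 41.1 | 91.5% | 74% |
| 48 months from randomization (section 5.6) | 0.583 / 0.321 | 36.9 | 89.1% | 37% |
| 42 months from randomization | 0.554 / 0.299 | 34.8 | 87.7% | 20% |

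**3. Would waiting recover the events?** Without the limit, 39 expected events are reached about 17 months after accrual closes. With the 48-month reading this takes about 29 months, some 8 months past December 2021; the ceiling is 40.8 × [(1 − 0.360) + (1 − 0.640)] = 40.8. With the 42-month reading the ceiling is 40.8 × [(1 − 0.409) + (1 − 0.677)] = 37.3, so 39 would not be expected however long one waits.

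**4. Sensitivity to dropout.** Treat loss as gradual censoring of all 96 patients, at exponential rate η = −ln(0.85)/T, where T is the month by which 15% are lost. Each arm's probability becomes λ/(λ+η) × mean[1 − exp(−(λ+η) × min(t, cap))].

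| Loss model | No limit | 48 months | 42 months |
|---|---|---|---|
| 15% by month 24 | 41.7 | 38.3 | 36.5 |
| 15% by month 51 | 45.0 | 40.9 | 38.7 |
| 15% by month 81 | 46.2 | 41.8 | 39.5 |
| No loss | 48.4 | 43.4 | 40.9 |

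The limit costs about 3 to 8 events in every row. Whether the total falls below 39 depends on the row.

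**5. Men whose PSA follow-up would stop early.** Share with potential follow-up beyond the limit × average probability of still being progression-free:
- 42 months: 0.65 × (0.409 + 0.677)/2 = 0.65 × 0.543 = 35%, about 29 of 81.6.
- 48 months: (81 − 48)/60 × (0.360 + 0.640)/2 = 0.55 × 0.500 = 27.5%, about 22 of 81.6.

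**The case against.** **No text says 42 months from randomization.** Footnote 9 defines 42 as the length of the study. From April 2015 that ends about October 2018, before the 80 patients reported by April 2019, so it cannot be operating literally. Section 5.6 counts from end of treatment. The 48-month rows are therefore the better supported reading, and the 42-month rows show what happens if a site counts from entry. This shifts the weight to the smaller effect but leaves the contradiction.

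**The effect is small.** On the 48-month reading power is 89.1% against a planned 90%. The plan describes censoring lost patients at their last PSA, which is closer to gradual loss, and there the totals are 38.3 to 41.8. This stands: the main damage is to the event trigger and to uniform follow-up, with little lost in power.

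**Late events may be fewer than a constant hazard implies.** Exponential extrapolation puts control FFPP at 18% by month 81, whereas section 1.3.3 cites durable responses in 30–40%. I fitted a control curve p + (1 − p)exp(−kt) through 60% at two years, with p = 0.3 or 0.4 and the same HR. The 48-month limit then costs 2.1 or 1.2 events. But the unlimited totals are then only 35.4 and 32.6, which makes a fallback rule more necessary.

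**Other text would keep PSA going.** Footnote 4 continues 3-monthly PSA until progression for men who come off study early, and the column heading and footnote 8 have no month limit. These make stopping less likely. However, footnote 4 gives toxicity as its example and does not clearly cover a man reaching study end, and footnote 9 says explicitly that the earlier of the two applies.

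**Section 9.6 is a hard stop.** Read that way, the 29-month wait would run past database lock. At a 24-month lock the 48-month reading gives 37.8 events and 89.7% power. But 9.6 conflicts with the 21 months elsewhere and does not say how to analyse fewer than 39 events.

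**Conclusion.** The concern holds. Footnote 9 and sections 5.2 and 5.6 carry a limit from the superseded design that contradicts the synopsis and section 10.4.1, and nothing in the documents cancels it. If applied, and with 15% of patients non-evaluable, it removes 41.1 − 36.9 = about 4 expected events (48-month reading) to 41.1 − 34.8 = about 6 (42-month reading) and makes reaching 39 by December 2021 unlikely. Power falls by about 2 to 4 percentage points. Gradual dropout brings the count back to or above 39 in several cases.

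These are design-based expectations under exponential times and uniform accrual, not a forecast: section 10.4.1 says 96 also reflects events, follow-up and dropout to date, which are not shown. The contradiction itself does not depend on any of these assumptions. It should be fixed, because primary-endpoint data not collected cannot be recovered and the correction is cheap.

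**What to change.** 1. In footnote 9 and sections 5.2 and 5.6, replace the 42-month limit with: *PSA every 3 months until PSA progression or the primary-analysis data cutoff*. In footnote 9, replace the 18+24-month study length with 60+21 months.
2. Reconcile section 9.6 (24 months after the last enrolment) with the synopsis and section 10.4.1 (21 months).
3. In section 10.4.1 state one cutoff: the 39th PSA-progression event or, if fewer than 39 have occurred by a fixed calendar date, analysis at that date with power reported at the observed event count. This is needed even without the limit, since the chance of fewer than 39 by December 2021 is then still about 100% − 74% = 26%.

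**Cost.** Wording in five places, with no new patients or procedures. About 22 to 29 progression-free men continue 3-monthly PSA, which the revised design already assumes. Section 11.3 requires the consent form to describe the likely follow-up, so the sponsor should check whether it quotes the old duration and needs updating.
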